3.2.2.3 Vital Signs

Vital signs will include resting BP, pulse, and respiratory rate measurements. For further information on vital signs refer to Section 8.2.2 in the CSP.

For information on how AEs based on vital sign results should be recorded and reported, refer to Section 8.3.5 in the CSP.

Notable changes from pre-dose at each post-dose time point for vital sign parameters will be identified. The predefined criteria for notable changes in vital signs values are displayed in [Table 1](#)

Table 1 Vital sign notable change predefined criteria

Vital sign		Observed value	Notable change from baseline
Systolic BP (mmHg)	High	≥ 140	Increase of ≥ 20
	Low	< 90	Decrease of ≥ 20
Diastolic BP (mmHg)	High	≥ 90	Increase of ≥ 10
	Low	< 60	Decrease of ≥ 10
Pulse Rate (bpm)	High	≥ 100	Increase of ≥ 20
	Low	< 50	Decrease of ≥ 20
Respiratory Rate (breaths/min)	High	> 20	
	Low	< 12	

BP = Blood pressure.

3.2.2.4 Electrocardiograms

Triplicate 12-lead ECGs will be performed after the participant has been resting in a supine position for at least 10 minutes, at the visits outlined in the SoA in [Appendix A: Schedule of Activities](#). For further information on ECGs refer to Section 8.2.3 in the CSP.

Digital ECGs performed at site will be transferred to Clario (ERT), where they will be centrally read and stored. A digital ECG machine that automatically calculates the heart rate and measures PR, RR, QRS, QT, and QTcF intervals will be used. Interpretation of the clinical safety digital ECG findings will be reviewed and confirmed by the investigator, classified as normal/abnormal and whether clinically significant, and recorded in the eCRF.

For information on how AEs based on ECG results should be recorded and reported, refer to Section 8.3.5 in the CSP.

Potentially clinically significant (PCS) ECG values will be identified from third party vendor data. The predefined criteria (based on severity) for PCS ECG values are displayed in [Table 2](#).

Table 2 PCS ECG predefined criteria

Variable	Unit	Outside lower limit if	Outside upper limit if	AZ extended reference range - low	AZ extended reference range - high	Treatment emergent increase if	Extended treatment emergent increase if
Heart rate	bpm	<50	>100	<45	>120	NA	NA
				<30	>150		
RR interval	ms	<600	>1200	<500	>1333	NA	NA
				<400	>2000		
PR interval	ms	<110	>220	<100	>240	>40	>60
QRS	ms	<75	>115	<70	>120	>15	>30
QT	ms	<320	>450	<300	>480	>30	>60
					>500		
QTcF	ms	<320	>450*	<300	>480*	>30*	>60*
					>500*		

ms = milliseconds, bpm = beats per minute, NA= not applicable.

*Cut-off values for categorical analyses as recommended by ICH E14 (Note, more than one category for high range increases in QT/QTc values)

Note, no standard criteria are established for treatment emergent increases or decreases in RR intervals or heart rates, or for treatment emergent decreases in PR, QRS or QT/QTc intervals

Note, lower and upper RR interval limits and low and high RR interval reference ranges (all in ms), represent respectively the upper and lower heart rate limits and high and low heart rate reference ranges (all in bpm)

3.2.2.5 Clinical Safety Laboratory Assessments

Blood and urine samples for determination of clinical chemistry, haematology, and urinalysis will be taken at the visits indicated in the SoA in [Appendix A: Schedule of Activities](#).

Additional safety samples may be collected if clinically indicated at the discretion of the investigator. The date, time of collection, and results (values, units, and reference ranges) will be recorded on the appropriate eCRF.

The clinical chemistry, haematology, and urinalysis will be performed at a central laboratory. Sample tubes and sample sizes may vary depending on laboratory method used and routine practice at the site.

In addition, samples will also be collected for analysis of the following parameters:

- Screening samples for parameters needed to confirm eligibility:
 - For women only: serum pregnancy test (only included in listings).
- Samples for the determination of cystatin C by a central laboratory at the visits indicated in the SoA in [Appendix A: Schedule of Activities](#).

Laboratory variables will be measured as indicated in [Table 3](#).

Table 3 Laboratory Safety Variables

Haematology/Haemostasis (whole blood) ^a	Clinical Chemistry (serum or plasma) ^a
White blood cell (WBC) count	Serum sodium (Na ⁺)
Red blood cell (RBC) count	Serum potassium (K ⁺)
Haemoglobin (Hb)	Serum urea
Haematocrit	Blood urea nitrogen (BUN)
Neutrophils absolute count	Serum creatinine
Lymphocytes absolute count	Estimated glomerular filtration rate (eGFR), calculated by CKD-EPI formula ^b
Monocytes absolute count	Uric acid
Eosinophils absolute count	Albumin
Basophils absolute count	Calcium
Platelets	Phosphate
International normalised ratio (INR) (including prothrombin time, required to calculate INR)	Alkaline phosphatase (ALP)
	Alanine aminotransferase (ALT)
Urinalysis	Aspartate aminotransferase (AST)
Glucose	Total bilirubin (TBL)
Erythrocytes	Creatinine kinase (CK)
Protein	Chloride (Cl ⁻)
Albumin	Magnesium (Mg ⁺)
Creatinine	Glucose (fasting, refer to Section 5.3.1 of the CSP)
	HbA1c (fasting, refer to Section 5.3.1 of the CSP)
Other assessments ^a	Cholesterol and lipids (fasting, refer to Section 5.3.1 of the CSP)
Cystatin C (serum)	
Serum pregnancy test (women only, at screening)	

NB. In case a participant shows an AST or ALT $\geq 3 \times$ ULN together with total bilirubin $\geq 2 \times$ ULN, refer to Appendix E in the CSP.

^a Central laboratory for all visits.

^b eGFR will be calculated by the central laboratory analysing the sample, using the CKD-EPI formulae in both ways, based on cystatin C and based on creatinine.

At each visit (except for screening), the geometric mean of the triplicate urine albumin and urine creatinine samples will be computed and used for summarising the parameters. If any of the samples for triplicate urine albumin or urine creatinine are missing, then the geometric mean will be calculated based on the available samples for the triplicate.

3.2.2.6 Echocardiography Assessment of Cardiac Structure and Function

An assessment of cardiac structure and function using echocardiography will be performed during the Screening period and at Week 12. The examination is non-invasive and prior preparation is not required.

The following parameters will be assessed:

- The left ventricular ejection fraction (LVEF) (%)
- Overall echocardiography evaluation (normal/abnormal)

- Left ventricular wall motion
- Method of left ventricular volume/ejection fraction calculation
- Mitral valve evaluation
- Aortic valve evaluation
- Tricuspid valve evaluation
- Pulmonic valve evaluation
- Mitral valve closure to open time (s)
- Tricuspid valve closure to open time (s).

3.2.2.7 Events of special interest

Changes in fluid-related measures (weight gain or BNP) meet the defined threshold to be considered as an event of special interest if they are as follows:

- BNP is increased > 100% from baseline and is greater than 200 pg/mL in a participant without atrial fibrillation or
- BNP is increased > 100% from baseline and is greater than 400 pg/mL in a participant with atrial fibrillation or
- More than 3% increase in study site body weight (at least 2.5% of which must be from total body water [increase of at least 2.5% in total body water from baseline as a percentage of baseline study site body weight] as measured by bioimpedance) from start of treatment (Day 1)

3.2.3 Exploratory Variables

3.2.3.1 Bioimpedance Spectroscopy

BIS will be performed at the site at the time points specified in the SoA in [Appendix A: Schedule of Activities](#) to monitor body fluid volumes: total body water, extracellular fluid, and intracellular fluid.

3.2.3.2 Pharmacokinetics

Plasma samples will be collected for measurement of plasma concentrations of zibotentan and dapagliflozin, and exploratory zibotentan metabolite evaluation, as specified in the SoA in [Appendix A: Schedule of Activities](#).

A sub-group of at least 20% of the overall study population will have 4 PK samples taken in addition to the pre-dose sample, spread over 4 different time points (0.5-1.0 h, 1.5-2.0 h, 2.5-3.0 h and 3.5-4.5 h post-dose). Zibotentan and dapagliflozin concentrations will be measured separately. As indicated in the SoA in [Appendix A: Schedule of Activities](#), the additional samples will be taken at Visit 4. For further information on the PK sub-study refer to Section 8.5.1.1 in the CSP.

Samples for determination of zibotentan and dapagliflozin concentrations in plasma will be assayed by Labcorp Bioanalytical Services LLC on behalf of AstraZeneca, using appropriately validated bioanalytical methods. Zibotentan and dapagliflozin plasma concentrations will be measured separately. Full details of the analytical methods used will be described in a separate Bioanalytical Report.

Samples for zibotentan metabolite evaluation will be analysed by AstraZeneca. Results from this analysis may not be reported in the CSR.

Drug concentration information that would unblind the study will not be reported to investigative sites or blinded personnel until the study has been unblinded.

Incurred sample reproducibility analysis, if any, will be performed alongside the bioanalysis of the test samples. The results from this evaluation, if performed, will be reported in a separate Bioanalytical Report.

3.2.3.3 Pharmacodynamics

Urinary and serum/plasma parameters will be measured during the study for the evaluation of the exploratory endpoints.

The following parameters will be measured from the blood samples collected for safety (from Visit 2 to 8, analysed at a central laboratory, see Section 3.2.2.5):

- Plasma/serum K^+ , Na^+ , uric acid, BUN, and fasting plasma glucose as part of clinical chemistry.
- Haematocrit and haemoglobin, as part of haematology.

Urine samples will be collected and analysed by a central laboratory for the determination of the exploratory urinary parameters at the time points specified in the SoA in [Appendix A: Schedule of Activities](#).

The urine samples collected on visit days for the analysis of UACR (see Section 3.2.1.1) will be split, so that they can also be used for the determination of Na^+ , K^+ , uric acid, urea, glucose, creatinine, osmolality and cortisol levels. Cortisol levels will not be reported in the CSR.

Blood samples will be collected at the time points specified in the SoA in [Appendix A: Schedule of Activities](#) and analysed by a central or local laboratory for the determination of the following parameters:

- Cystatin C, ET-1, ELDP, CT-proET-1, copeptin, NT-proBNP, and BNP. Results for ET-1, ELDP, CT-proET-1 and copeptin will not be reported in the CSR.
- Fasting plasma glucose (for fasting conditions, refer to Section 5.3.1 of the CSP).

4 STATISTICAL METHODS

4.1 Data Quality Assurance

All tables, figures and data listings to be included in the report will be independently checked for consistency, integrity and in accordance with standard Parexel procedures.

4.2 General Presentation Considerations

4.2.1 Study Period

The following study periods are defined (if the specified visit did not take place, the date for planned visit should be used):

- Overall study period – from date of Visit 1 to date of Visit 8
- Screening period – from date of Visit 1 up to the day before Visit 2; this can be up to approximately 4 weeks in duration prior to randomisation
- Treatment (Interventional) period – from date of Visit 2 to date of Visit 7
- On-treatment period – from the same date as the first administration of study intervention until the earliest of: 28 days after last dose of zibotentan/placebo and/or dapagliflozin/placebo; end of study; lost to follow-up; and withdrawal of consent
- Off-treatment period – from more than 28 days after the last dose of study intervention
- Follow-up period – from day after Visit 7 to date of Visit 8

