Digital 12-lead safety ECG	X	X	X	X	X	X	X	X	ECGs will be centrally read. ECG read out from Visit 2 to be reviewed by the investigator before randomisation as central report will not be available on the day. Unscheduled ECGs may be added if clinically indicated.	Section 8.2.3	

Procedure	Screening	Interventional period						Follow-up	Notes	Details in CSP Section/Appendix
		2	3	4	5	6	7 (ED)			
Visit	1	2	3	4	5	6	7 (ED)	8		
Week	-4	0	1	3	6	9	12	14		
Day	-28	1	8	22	43	64	84	98		
Day Visit Window	+7/ -14		±1	±2	±2	±2	±2	±3		
Clinical chemistry and haematology (central laboratory)	X	X	X	X	X	X	X	X	Central laboratory results must be reviewed by investigator within 48 hours from receipt of result, and eGFR and creatinine calculations made, and participant discontinued if required. Clinical chemistry includes creatinine and eGFR calculation using the CKD-EPI formula in both ways: based on cystatin C and based on creatinine.	Sections 8.1.2.2 and 8.2.4
Urinalysis (central laboratory)	X	X		X			X	X		Section 8.2.4
HbA1c, cholesterol and lipids (central laboratory)	X	X					X	X		Section 8.2.4
Study intervention										
Study intervention dispensed		X		X	X	X				Section 6.2, 6.3, 6.4
Study intervention account				X	X	X	X			Section 6.2, 6.4
Study intervention intake at the clinic		X		X		X			Between the clinic visits and at Visits 3, 5 and 7, participants will take their study intervention at home. At Visits 4 and 6, study intervention will be taken in the clinic irrespective of participation in the PK sub-study.	Section 6.2, 6.3, 6.4

Procedure	Screening	Interventional period						Follow-up	Notes	Details in CSP Section/Appendix
		1	2	3	4	5	6			
Visit	1	2	3	4	5	6	7 (ED)	8		
Week	-4	0	1	3	6	9	12	14		
Day	-28	1	8	22	43	64	84	98		
Day Visit Window	+7/ -14		±1	±2	±2	±2	±2	±3		
Pharmacokinetics										
4-hour PK blood sample profile				X					Total of 5 samples, spread over 5 time points: Pre-dose, 0.5-1.0 h, 1.5-2.0 h, 2.5-3.0 h, 3.5-4.5 h post-dose. Performed in the morning. Dose taken at clinic. Participants to arrive fasted at clinic (light breakfast provided). Participants to stay at clinic until last PK post-dose sample has been taken. Zibotentan and dapagliflozin plasma concentrations will be measured separately. If participants or investigators do not wish to participate in this sub-study, only one pre-dose sample (separate tubes for zibotentan and dapagliflozin) will be taken instead of the whole profile.	Section 8.5.1.1

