3.2.2 Safety Variables

Safety will be assessed by descriptive analysis of AEs (including serious adverse events [SAEs] and adverse events leading to the discontinuation of study intervention [DAEs]), vital signs, ECGs, laboratory assessments, echocardiography assessments and events of special interest.

Treatment-emergent throughout this document has the meaning of an event such as an AE or laboratory/ECG/vital sign value outside of predefined ranges occurring during on-treatment as defined in Section 4.2.1 and Section 4.11.2.

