For continuous variables, descriptive statistics will include the number of non-missing observations (n), mean, standard deviation (SD), median, minimum and maximum. For log-normal variables, the geometric mean (GeoMean) and coefficient of variation (CV) will be presented in addition to those already specified for continuous variables. Continuous data that are expected to be skewed (e.g. duration of exposure, time on study and laboratory variables) will be presented in terms of the maximum, upper quartile, median, lower quartile, minimum and number of observations. The minimum and maximum will be reported to the same number of decimal places as the raw data recorded in the database. The mean, median, lower quartile and upper quartile will be reported to one more decimal place than the raw data recorded in the database. The SD will be reported to two more

decimal places than the raw data recorded in the database. In general, the maximum number of decimal places reported shall be four for any summary statistic.

Categorical variables will be summarised using frequency counts and percentages. Percentages will be presented to one decimal place. Percentages will not be presented for zero counts. Percentages will be calculated using the number of non-missing observations as the denominator, unless otherwise specified in the TLF mock shells. If sample sizes are small, the data displays will show the percentages, but any textual report will describe frequencies only.

P-values greater than or equal to 0.001, in general, will be presented to three decimal places. P-values less than 0.001 will be presented as “<0.001”.

Confidence intervals will be presented to one more decimal place than the raw data.

Data will be summarised by visit, as appropriate. For information on analysis visit windows, please refer to Section 4.2.3

‘Baseline’ is defined as the last non-missing value obtained prior to or on the same date as the administration of the first dose of study treatment, unless otherwise stated. For participants without a first dose, the last non-missing value obtained prior to or on the same date as the randomisation date will be used for ‘baseline’. ‘End of Study’ is defined as the last available post-treatment assessment. ‘Study Day’ will be calculated relative to the date of first dose of study treatment i.e.:

if Assessment Date < Date of First Dose of Study Treatment, then

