4.11 Safety Evaluation

All safety summaries and analyses will be based upon the Safety Analysis Set as defined in Section 4.6 and the on-treatment period as defined in Section 4.2.1, unless otherwise specified. Safety summaries will be presented by treatment arm.

Change from baseline will be calculated as the difference between the post-dose value at each time point and the last non-missing value prior to or on the same date as administration of the first dose of investigational products.

Individual safety and tolerability data will be provided in data listings and summarised as appropriate by treatment and overall. Continuous variables (laboratory parameters, ECG, and vital signs) will be summarised using descriptive statistics (n, mean, SD, minimum, median, and maximum) as appropriate by scheduled assessment time point. Where applicable, data will be summarised for the observed value, and for the corresponding change from baseline/screening. Categorical variables will be summarised in frequency tables (counts and percentage) as appropriate by scheduled assessment time point.

Changes from baseline in categorical data will be summarised using shift tables where appropriate.

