4.11.4 Clinical Laboratory Evaluation

The following summaries will be provided:

- A summary, which will cover n, mean, SD, minimum, Q1, median, Q3, and maximum, of the observed values and change from baseline for all clinical chemistry (including cystatin C), haematology and quantitative urinalysis parameters by treatment arm and time point
- A summary of baseline to maximum observation on treatment in each clinical chemistry (including cystatin C) and haematology laboratory parameter by treatment arm (shift table)

- A summary of baseline to minimum observation on treatment in each clinical chemistry (including cystatin C) and haematology laboratory parameter by treatment arm (shift table)
- A plot of ALT versus total bilirubin, expressed as multiples of upper limit of normal (ULN)
- A plot of AST versus total bilirubin, expressed as multiples of ULN
- A summary of the number and percentage of participants reporting maximum on-treatment ALT and AST by maximum total bilirubin for assessing Hy's Law criteria
- A summary of individual participant data for participants with Potential Hy's Law i.e. participants with combined ALT or AST, and bilirubin elevations
- A summary of key participant information for participants with treatment-emergent changes in laboratory parameters (refers to clinical chemistry and haematology, other laboratory parameters are in supportive listings) outside of pre-defined criteria
- A summary of treatment-emergent laboratory changes (see [Appendix C: Treatment-Emergent Changes in Relevant Laboratory Parameters](#))
- A summary of baseline versus maximum value on treatment for urinalysis by treatment arm (shift table)
- A summary of treatment-emergent urinalysis changes

Treatment-emergent changes in relevant laboratory parameters outside pre-defined criteria for this study are provided in [Appendix C: Treatment-Emergent Changes in Relevant Laboratory Parameters](#). Treatment-emergent urinalysis changes are defined as: negative/trace at baseline to ++, +++, +++++ at any visit after baseline or an increase of at least ++, for example + to +++, ++ to +++++.

By-participant listings of all laboratory data will be provided including participant identifier, treatment, age, sex, race, visit, category, lab test name, result, change from baseline (where appropriate) and standard units. Laboratory reference ranges will also be listed and out of range values will be flagged.

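### Pre-dose Visit 2 laboratory and ECG values fall inside the on-treatment period, so some are counted as treatment-emergent or as on-treatment extremes

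*SAP*

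**What the plan says.** - **On-treatment period (SAP 4.2.1):** it runs "from the same date as the first administration of study intervention until the earliest of" several end dates. The start is a calendar date.
- **Baseline (SAP 4.2.2):** the "last non-missing value obtained prior to or on the same date as the administration of the first dose of study treatment". This too is a calendar date, and it includes Day 1.
- **Treatment-emergent (SAP 3.2.2):** for these data, a "laboratory/ECG/vital sign value outside of predefined ranges occurring during on-treatment as defined in Section 4.2.1 and Section 4.11.2". The value need not be new since baseline or post-dose.
- **Default for safety outputs (SAP 4.11):** "the on-treatment period as defined in Section 4.2.1, unless otherwise specified".
- **Shift tables (SAP 4.11.4):** "A summary of baseline to maximum observation on treatment in each clinical chemistry (including cystatin C) and haematology laboratory parameter by treatment arm", and a matching table for the minimum. Neither excludes the baseline record.
- **Timing at Visit 2:** the first dose follows randomisation on Day 1 (Protocol 4.1; SAP 3.1). The Protocol schedule has the "ECG read out from Visit 2 to be reviewed by the investigator before randomisation", so that ECG is pre-dose.

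Elsewhere the SAP does separate the two periods. Vital-sign notable changes are tied to post-dose time points (SAP 3.2.2.3), treatment-emergent urinalysis changes to visits after baseline (SAP 4.11.4), and the PK baseline to date and time (SAP 4.12.1). SAP 4.15 does not mention the overlap.

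**The concern.** Day 1 belongs to both periods, and the Visit 2 assessments and first dose share that day. A finding that was present before any drug was taken can then be tabulated as arising on treatment. In the shift tables, one record can be both the baseline and the on-treatment extreme it is compared with. In a dose-ranging trial of a combination, the safety tables should separate what participants brought to the trial from what appeared after dosing. Two programmers could also produce different tables from the same SAP, one using the literal rule and one dropping the baseline record by habit.

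**Working it through.** The plan states no figure on this point, so there is none to reproduce. The first three steps trace a Visit 2 value through the rules. The last two give an illustrative size.

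**1. Absolute laboratory limits (SAP Appendix C).** Take an invented participant with potassium 6.1 mmol/L at Visit 2, then 5.0, 5.1, 5.0, 4.9, 5.0 and 5.1.
- Literal rule: on-treatment maximum 6.1, so the limit of 6.0 or above is flagged.
- Without the pre-dose record: maximum 5.1, no flag.

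Exposure differs by parameter. Screening excludes sodium below 135 mmol/L and haemoglobin below 10 g/dL (Protocol 5.2, criteria 11 and 19b). Reaching the low limits (sodium below 130, haemoglobin below 9) at Visit 2 therefore needs a fall of more than 5 mmol/L or 1 g/dL since screening. Potassium, creatine kinase and sodium above 150 mmol/L have no matching numeric entry limit, so they are the realistic cases. Creatinine limits are multiples of baseline: a baseline value has ratio 1.0 and cannot trigger them.

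**2. Absolute ECG limits (SAP Table 2).** Eligibility excludes QTcF above 470 ms (Protocol 5.2, criterion 13), but the first limit is above 450 ms. A value of 451-470 ms at Visit 2 is eligible and exceeds that limit before dosing. Increases of more than 30 or 60 ms are safe, because the baseline record gives a change of zero.

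**3. Shift tables (SAP 4.11.4).** With a Day 1 baseline B and later values X1 to X6:
- max(B, X1, ..., X6) ≥ B, so the maximum table has no high-to-normal cell.
- min(B, X1, ..., X6) ≤ B, so the minimum table has no low-to-normal cell.

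A participant high at baseline and normal at every later visit appears as high-to-high in the maximum table and correctly as high-to-normal in the minimum table. Urinalysis has only a baseline-to-maximum shift table, subject to the same default period.

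**4. Size, laboratory.** Chemistry and haematology are scheduled at Visits 2 to 8, so the literal rule uses 7 values and a post-dose rule 6. Assume no drug effect, 5% above the upper limit at each visit (c = 1.645 on the standard normal scale) and within-person correlation ρ. The chance of being high at Visit 2 and at no later visit is

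∫ φ(u) [1 − q(u)] q(u)^6 du, with q(u) = Φ((c − √ρ·u)/√(1 − ρ)).

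| ρ | Of those high at Visit 2 | Of all participants |
|---|---|---|
| 0.5 | 35% | 5% × 0.349 = 1.7% |
| 0.7 | 22% | 5% × 0.220 = 1.1% |
| 0.8 | 16% | 5% × 0.157 = 0.8% |

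That is about 1 to 3 people in an arm of 166 (0.8% × 166 = 1.3; 1.7% × 166 = 2.8) and about 1 in the arm of 83.

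For rarer limits such as those in Appendix C, take an assumed 1% chance per visit. The share of participants with any flag falls from 6.8% (7 values) to 5.9% (6 values) if visits are independent, since 1 − 0.99^7 = 0.068 and 1 − 0.99^6 = 0.059. With ρ = 0.8 it falls from 3.3% to 3.1%.

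**5. Size, QTcF.** Simulation with total SD 20 ms, values limited to 470 ms at Visits 1 and 2, six later ECGs and no drug effect. Means and SDs are assumptions.

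| Mean / within-person SD (ms) | Above 450 at Visit 2 | Above 450 at Visit 2 only |
|---|---|---|
| 415 / 8 | 3.5% | 0.6% |
| 420 / 10 | 5.8% | 1.1% |
| 425 / 12 | 9.0% | 1.9% |

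The last column is the net effect. The others would be flagged anyway from a later ECG.

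**The case against.** The strongest reply is that this is a wording gap with little consequence. The tables are descriptive, no hypothesis test depends on them, and the overlap applies to every arm. By-visit tables are protected because the Week 1 window in SAP Table 5 opens on Day 2. SAP 4.11 computes change from baseline from the post-dose value, and a baseline-to-maximum table can be read as comparing two separate records. Table 2 uses the term treatment-emergent only for increases, not for the absolute limits. Output shells, which are not in these documents, may already drop the baseline record. Finally, the Visit 2 blood draw is not labelled pre-dose; that is inferred from clinic dosing following the assessments (Protocol 5.3.1).

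Most of this stands as a limit on size and scope. It does not remove the point. SAP 3.2.2 and 4.11 together bring out-of-range values during the date-defined period into the on-treatment summaries, and nothing written for chemistry, haematology or absolute ECG limits takes the pre-dose record out. The SAP adds that qualifier for other data, so its absence here cannot be assumed to be understood.

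A reader might go further in three ways that the documents do not support:
- **That the tables cannot show improvement at all.** For chemistry and haematology the opposite shift table and the by-visit summaries still can.
- **That ECG values enter an on-treatment maximum or minimum.** SAP 4.11.5 plans no such ECG table. The main effect is on the potentially clinically significant counts.
- **That the size is 14%, 16-35% or 3.5-9%.** With no drug effect the pre-dose value is the largest of seven in 1/7 = 14% of participants, but a maximum within the normal range changes no cell. The 16-35% applies only to those high at baseline. The 3.5-9% includes people who would be flagged anyway.

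**Conclusion.** The point holds. As written, the rule counts pre-dose Visit 2 laboratory and ECG values as on-treatment, which gives wrong counts for absolute limits and blocks one direction of recovery in each chemistry and haematology shift table. The effect is small: about 0.8% to 1.7% of participants per laboratory parameter in one shift table, and 0.6% to 1.9% for QTcF above 450 ms. These figures rest on assumed prevalences, correlations, means and SDs, with no drug effect, and on Visit 2 blood being drawn before dosing. The pre-dose timing is explicit for the ECG and implied for the blood sample.

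Because Visit 2 values precede treatment, the error is expected alike in all arms. It mislabels pre-existing findings and dilutes contrasts; it does not favour an arm. Unaffected are creatinine multiples, ECG increases, fluid-related events, by-visit tables, treatment-emergent urinalysis changes, vital-sign notable changes and the primary UACR analysis.

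**What to change.** Add to SAP 4.2.1 and 4.11: for laboratory and ECG data, the baseline record and any other value taken before the first dose, judged by date and time as SAP 4.12.1 already does for PK, are excluded from on-treatment, treatment-emergent, potentially clinically significant and maximum/minimum derivations. Where the time is missing, scheduled Visit 2 records are treated as pre-dose. Genuine post-dose values on Day 1 stay in. The same-date start stays for adverse events, which are collected only after the first dose.

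Two simpler filters are less good. Starting these data at study day 2 would discard real post-dose Day 1 values. Dropping only the flagged baseline record would leave an earlier same-day repeat in the on-treatment data.

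The cost is one sentence and a program filter. If the programs already do this, the sentence records it.
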